# **9.2.4.3** *Patients*

# Patient enrolment by M3 Global Research:

Patients in Germany, France and Greece will be recruited by IQVIA's trusted and assessed vendor – M3 Global Research, from the vendor representative panel. As in the prescribers' surveys, patients will be first contacted by email, then by phone if they do not respond to the email. Their recruitment will be done as follows:

- The sampling of patients will follow a randomised sampling method which ensures
  the representativeness of the population being reached in order to limit selection bias
  which is commonly found in opportunistic selection method. However, only patients
  who consent will participate, which brings some degree of selection bias that cannot
  be ruled out.
- The M3 Global Research team will randomly contact patients by emails or phone calls when needed, according to their sub-groups (see Section 9.2.1.3 for further details on patient selection). Survey background and objectives, the contact

Template No.: RWI\_TP\_EPI0016 Revision 1 Reference: RWI\_WI\_EPI0005

Protocol/Study No: SC02 EMA/2018/19/PE

Page 34 of 92

information for questions, and the proposed compensation will be explained at this stage.

- If they agree to participate in the survey, they will receive a link to access the survey and the instructions for web questionnaire completion.
- If the questionnaire is not completed in the IQVIA Primary Intelligence EDC system, the patients will be sent regular email/phone reminders.
- The M3 Global Research telephone team can call the patients if they see that they get stuck during the course of completing the survey, or if they stop for any reason they might provide technical help or other advice. Patients will also have the option to contact M3 directly if they need support. These interactions cannot be scripted.
- A screening log is maintained to follow-up the inclusion of patients in the survey over time.

If necessary, i.e. if the target number of responders is still not reached, recruitment will continue to achieve the targeted study sample size A patient will be considered unreachable if he/she has been contacted between 3 and 5 times without any answer being received.

The number of patients that are eligible for inclusion in the study and the survey response rate will be monitored regularly.

# Patient enrolment by GLocalMind:

Patients in Sweden and Poland will be recruited by IQVIA's trusted and quality assessed vendor – GLocalMind, from the vendor representative partner panel.

Patients will be first contacted via both email and GLocalMind's panellist member app (linked to their panel portal), then by phone if they do not respond to the email and app. Their recruitment will be done as follows:

- The sampling of patients will follow a randomised sampling method which ensures
  the representativeness of the population being reached in order to limit selection bias
  which is commonly found in opportunistic selection method. However, only patients
  who consent will participate, which brings some degree of selection bias that cannot
  be ruled out.
- The GLocalMind team will randomly contact patients by emails or via their app when needed, according to their sub-groups. Survey background and objectives, the contact information for questions, and the proposed compensation will be explained at this stage.
- If they agree to participate in the survey, they will receive a link to access the survey and the instructions for web questionnaire completion.
- If the questionnaire is not completed, the patients will be sent a reminder by email one week after the invite was sent out.

Template No.: RWI\_TP\_EPI0016 Revision 1 Reference: RWI\_WI\_EPI0005

Protocol/Study No: SC02 EMA/2018/19/PE

Page 35 of 92

- If the target is not achieved, a second reminder by phone will be conducted approximately 1.5 weeks after the invite was sent out.
- The GLocalMind telephone team can call the patients if they see that they get stuck during the course of completing the survey, or if they stop for any reason they might provide technical help or other advice. Patients will also have the option to contact GLocalMind directly if they need support. These interactions cannot be scripted.
- A screening log is maintained to follow-up the inclusion of patients in the survey over time.

If necessary, i.e. if the target number of responders is still not reached, recruitment will continue to achieve the targeted study sample size A patient will be considered unreachable if he/she has been contacted between 3 and 5 times without any answer being received.

The number of patients that are eligible for inclusion in the study and the survey response rate will be monitored regularly.

# 9.2.4.4 Selection criteria of the booster country

When the list (prescribers, pharmacists or patients) is exhausted in any target country (France, Germany, Greece, Poland, and Sweden) at any given time during the recruitment period and the overall sample size is not yet reached, recruitment will take place from another country from the list of target countries, to achieve the overall sample size.

The following criteria need to be fulfilled by the booster country, from the list of the participating countries in this survey, in order for further recruitment to take place:

- Any other country which meets the minimum sample size
- The list of prescribers, pharmacists or patients in that country is not yet exhausted

At this point, it is not possible to project which country(ies) may be suited to boost an exhausted country(ies), hence the above criteria will be followed to select suitable booster countries.

#### 9.3 Variables

# **9.3.1** Exposure Definition and Measures

No study medication is provided as part of participation.

#### 9.3.2 Outcome Definition and Measures

The number of prescribers/pharmacists/patients invited to participate will be managed through the computer software, which is used to send and manage the invitations, but not through the survey as such. After fieldwork completion we will provide a separate report containing recruitment data that can be used to analyse the participation rate.

Template No.: RWI\_TP\_EPI0016 Revision 1 Reference: RWI\_WI\_EPI0005

Protocol/Study No: SC02 EMA/2018/19/PE

Page 36 of 92

#### 9.3.2.1 Variables collected through the prescriber survey

The following variables will be collected through the prescribers' surveys:

- Variables related to prescriber's practice information:
  - o Demographic information (country)
  - o Gender (if available)
  - o Prescriber primary specialty
  - o Duration of practice in primary specialty (inclusive of specialty trainings)
  - o Practice setting (Office or hospital-based or both)
  - Experience with MTX in the once-weekly indications (number of patients treated with MTX)
- Variables related to the prescriber's receipt and awareness of the DHPC and EMs:
  - o Receipt and awareness of the DHPC
  - Receipt and awareness of the new or updated EMs for HCPs (checklist or guide)
  - o Awareness of the patient card
- Variables related to the knowledge of the risks of inadvertent overdose due to daily instead of weekly use
  - Knowledge of the dosing frequency of MTX in the treatment of indications requiring once-weekly dosing regimens
  - o Knowledge of the updated posology instructions and boxed warning
- Variables related to adherence to SmPC recommendations for oral and parenteral MTX-containing medicines with at least one indication requiring once-weekly dosing

# 9.3.2.2 Variables collected through the pharmacist survey

The following variables will be collected through the pharmacists' surveys:

- Variables related to pharmacists' practice information:
  - Demographic information (country)
  - o Gender (if available)
  - o Practice setting (community or hospital pharmacy)

Template No.: RWI\_TP\_EPI0016 Revision 1 Reference: RWI\_WI\_EPI0005

Protocol/Study No: SC02 EMA/2018/19/PE

Page 37 of 92

- Experience with MTX in the once-weekly indications (number of patients dispensed with MTX)
- Variables related to pharmacist's awareness of the patient card
- Variables related to awareness of the visual reminder on the outer packaging of oral and parenteral MTX-containing products
- Variables related to pharmacist knowledge of the patient card, the visual reminder on the outer packaging and the need to mark the day of intake for indications requiring once-weekly dosing regimens:
  - Knowledge of the patient card
  - o Knowledge of the visual reminder on the outer packaging
  - o Knowledge of the need to mark the day of intake for indications requiring once-weekly dosing regimens
- Variables related to the performed marking of the day of intake of MTX on the outer packaging for indications requiring once-weekly dosing regimens

### 9.3.2.3 Variables collected through the patient survey

The following variables are collected through the patient survey:

- Variables related to the patients treated with MTX
  - Patient age range
  - o Gender (if available)
  - Length of MTX treatment
  - o Indication for MTX treatment
  - o Prescriber setting (at first prescription) and prescriber specialty (at first prescription and in case of prescriber switching)
  - Mode of administration of MTX-containing products (oral/parenteral)
- Variables related to the patient card:
  - o Receipt and awareness of the patient card
  - o Knowledge of the purpose of the patient card
- Variables related to patient's awareness of the boxed warning in the package leaflet
- Variables related to patient's awareness of the visual reminder on the outer packaging of oral and parenteral MTX-containing products

Template No.: RWI\_TP\_EPI0016 Revision 1 Reference: RWI\_WI\_EPI0005

Protocol/Study No: SC02 EMA/2018/19/PE

Page 38 of 92

- Variables related to patient's knowledge of the once-weekly dosing frequency of MTX in the treatment of inflammatory diseases:
  - Knowledge of the once-weekly dosing frequency of MTX in the treatment of inflammatory diseases for his/her indication
  - Knowledge of the boxed warning in the package leaflet and visual reminder on the packaging of oral and parenteral MTX-containing products
  - Knowledge of symptoms of MTX overdose

## 9.3.3 Safety Measures

Not applicable.

## 9.3.4 Effectiveness Measures (*If Applicable*)

Not applicable.

## 9.3.5 Other Measures (If Applicable)

Not applicable.

#### 9.4 Data Sources

The survey is a primary data collection conducted through 3 questionnaires administered by web:

- A prescriber questionnaire
- A pharmacist questionnaire
- A patient questionnaire

### 9.4.1 Questionnaire description

The questionnaires will have a disclaimer and consent in the beginning. It collects information on demographics and eligibility of participants. It has included closed questions on the content of the EM, the question will be in order from the simplest to the hardest and from awareness to implementation. Furthermore, it is non-directing and not favouring social desirability, there is no possibility of coming back on previous answers to avoid information bias.

## 9.4.2 Qualitative interviews

Prior to initiation of the survey, IQVIA conducted qualitative interviews with 3 prescribers (2 from Germany and 1 from Sweden) and 3 pharmacists (2 from Germany and 1 from

Template No.: RWI\_TP\_EPI0016 Revision 1 Reference: RWI\_WI\_EPI0005

Protocol/Study No: SC02 EMA/2018/19/PE

Page 39 of 92

Sweden) in English language . Also, 3 patients were interviewed by IQVIA's trusted and assessed vendor, GLocalMind, (2 from France and 1 from Germany) in the local language. These interviews were carried out to gather more insights into the elements impacting the awareness, knowledge and behaviour of the population targeted with the risk-minimisation measures. The details of this qualitative approach were used as inputs to develop the protocol and the survey questionnaires (Annex 4. Summary of Qualitative Interviews).

#### 9.4.3 Questionnaire development

Each questionnaire i.e. prescriber, pharmacist and patient questionnaire was developed in English. The questionnaires were designed to be non-directing, clear, to avoid inducement of social desirability and had no self-evident answers. Each questionnaire included questions about screening criteria, demographics, receipt and awareness of MTX EMs, and knowledge about MTX risks. The prescriber and pharmacist questionnaire had additional questions about self-declared behaviour.

#### 9.4.4 Questionnaires translation

The translated versions of each questionnaire from English into local language will be done using the back and forth method (from English into local language and then from local language into English) to ensure an accurate translation. They will be then submitted to EMA for review and approval. Translation and back translation will be performed..

## 9.4.5 Questionnaire pilot testing

The objective of the prescriber and pharmacist questionnaires will be tested among 3 prescribers and 3 pharmacists, respectively, to make sure the right language and medical terms are used. The patient questionnaire will be tested by 3 non-physicians to check the understandability of the language.

## 9.4.6 Time to completion

Each prescriber, pharmacist and patient questionnaire's completion is estimated to take 10-15 minutes each.

## 9.4.7 Approaches for increasing response rates

People are increasingly contacted to participate in web or phone surveys. The overall response rate of participation remains low according to international studies (38-40). Holbrook et al. showed that the response rate to surveys continues to decline over time, but a lower rate does not appear to reduce the representativeness of a demographic survey (39). VanGeest et al. conducted a systematic review of 66 published reports on efforts to perform for improving response rates (41). Two general strategies were explored: incentives-based approaches and survey design-based approaches. Financial incentives, even little ones, were effective in improving physician response rates while non-monetary incentives were much

Template No.: RWI\_TP\_EPI0016 Revision 1 Reference: RWI\_WI\_EPI0005

Impact of EU label changes on methotrexate for weekly administration

Version 2.0 dated 21 February 2022

Protocol/Study No: SC02 EMA/2018/19/PE

Page 40 of 92

less effective. These measures include the use of a short questionnaire, and questionnaires personalised, and approved by professional associations.

In order to increase the response rate among prescribers, pharmacists or patients, a compensation fee will be proposed to prescribers, pharmacists or patients for their participation in the survey.

## 9.5 Study Size

## 9.5.1 Target Sample Size Calculations

The sample size formula based on the normal approximation to the binomial is the following:

$$n = \frac{P \cdot (1-P) \cdot \left(Z_{1-\alpha/2}\right)^2}{e^2},$$

Where P is the expected proportion, and e is the precision or the desired margin of error reflecting how many percentage points the results will differ from the real population value. For example, a 95% confidence interval (CI) with an 8% margin of error means that the statistic will be within 8 percentage points of the real population value 95% of the time. Z1-  $\alpha/2$  is the standard normal Z value corresponding to a cumulative probability of  $1-\alpha/2$  and reflecting the confidence level that will be used (e.g. if  $\alpha$  =.05 (i.e. 5% level of significance) then Z = 1.96). The range of p is between 0 to 1, and therefore the range of p(1-p) is between 0 to 1. The value of p that maximises p(1-p) is p = 0.5. Consequently, if there is no information available to approximate p, then p = 0.5 (i.e. 50%) can be used to generate the most conservative i.e. largest sample size.

Table 3 Margin of Error for 95% CI Based on Various Sample Sizes and Proportions of Interest

Margin of error for 95% CI (absolute precision)									
Proportion	8%	7%	6%	5%	4%	3%	2%		
10%	55	71	97	139	216	384	864		
30%	127	165	225	323	504	896	2,017		
50%	150	196	267	384	600	1,067	2,401		
70%	127	165	225	323	504	896	2,017		
90%	55	71	97	139	216	384	864		

Template No.: RWI\_TP\_EPI0016 Revision 1 Reference: RWI\_WI\_EPI0005

Protocol/Study No: SC02 EMA/2018/19/PE

Page 41 of 92

30

30

30

30

30

150

CI = confidence interval.

In each target population (prescribers, pharmacists and patients) the sample of 150 completed questionnaires can provide for a given proportion 50% and a confidence interval of 95% with a precision of 8%, i.e. that proportion in the target population could be between 42% and 58%. This sample (150) will be split among 5 countries for each of the surveys.

#### 9.5.2 **Sampling in the Participating Countries**

Ideally the sample of 150 prescribers, 150 pharmacists and 150 patients should be split among the countries based on the proportion of each target population (Table 4). However, such a sample distribution would lead to a too small number in some countries and a too large number in some others. As an alternative, an empirical split will be implemented to provide a number of questionnaires in each country which is both feasible and statistically interpretable. Such a sample will necessitate that the results of the study be weighted according to the real proportion of each target population in the countries.

**Country Prescribers Pharmacists Patients** France 30 30 30 Germany 30

30

30

30

150

**Table 4 Indicative Sample Distribution** 

30

30

30

150

#### 9.5.3 Sample Weighting

Greece

Poland

Sweden

Total

Since the relative weight of each country in the final sample will be different from its real relative weight in estimations, the extrapolation of the raw survey results to the overall target population would not be relevant without weighting. The survey results will be then weighted to reflect the real proportion of the prescribers, pharmacists, or patients in participating countries (or group of countries). Both unweighted (i.e. raw data) and weighted results will be presented in the report.

A weight variable will be applied to each statistical unit (i.e. a completed questionnaire) during the results calculation in order to correct any over-or under-sampling that may have

Template No.: RWI\_TP\_EPI0016 Revision 1 Reference: RWI\_WI\_EPI0005

Protocol/Study No: SC02 EMA/2018/19/PE

Page 42 of 92

occurred for a country or a target population. This weight variable will indicate how many unit(s) of the population of interest an observation will count in a statistical procedure. Its value will change per country and per target population. The weights will be normalised to obtain their sum for the whole dataset that will be equal to the sample size.

Since the weighted results are intended to represent their corresponding target population, the weighted results shall be used whenever available in the report. Unweighted results that ignore the sample weight can be biased for population quantities. But for more transparency, both unweighted and weighted results will be presented in the report. For the subsample information, the weighted results will not be provided as they do not make sense. As weighting is a statistical extrapolation by itself, it can only be conducted under the circumstances that such an extrapolation is valid. In the case of subsamples where the numbers are too low to be extrapolated for example, it makes sense not to weight. Therefore, the unweighted numbers which describe the sample – rather than the population – shall be used.

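### The blanket rule against weighting subsamples leaves those pooled over countries open to the country-mix distortion that weighting is meant to correct

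*Protocol*

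**What the plan says.** Section 9.5.2 replaces a proportional allocation with an empirical split, indicatively 30 respondents per country in each survey (Table 4), and draws the consequence: "Such a sample will necessitate that the results of the study be weighted according to the real proportion of each target population". Section 9.5.3 repeats the principle ("Unweighted results that ignore the sample weight can be biased for population quantities") and prefers weighted results wherever they exist. Full-sample results are to be shown both weighted and unweighted.

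The same section then makes an exception: "For the subsample information, the weighted results will not be provided as they do not make sense". The explanation is that weighting is an extrapolation and should be done only where extrapolation is valid: "In the case of subsamples where the numbers are too low to be extrapolated for example, it makes sense not to weight". It concludes that "the unweighted numbers which describe the sample – rather than the population – shall be used". No size limit is set, and subsamples within one country are not distinguished from subsamples pooled over several.

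**The concern.** The reason does not support the rule. A small subsample gives a wide interval. It does not change how many members of the target population a respondent from a given country stands for. A subsample drawn from several countries takes over the artificial allocation between them.

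The rule also applies in the wrong place. Inside a single country every respondent has the same weight, so weighted and unweighted percentages are identical and the rule changes nothing. It has effect only when countries are pooled, which is where section 9.5.2 says weights are needed.

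Pooled subsamples occur in this plan. Section 9.7.2.2 describes the profile of respondents with incorrect answers by specialty, practice setting, indication and other characteristics. Section 9.6.1 mentions skip patterns, and some follow-up items in Annex 5 (for example prescriber Q11 and Q13) concern only part of the sample. Items labelled for oral formulations only, or about materials that Table 1 marks as not applicable in some countries, may also count as subsample information, because the term is not defined.

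**Working it through.** **The plan's own figure.** Section 9.5.1 states that "the sample of 150 completed questionnaires can provide for a given proportion 50% and a confidence interval of 95% with a precision of 8" per cent. From n = P(1−P)z²/e²: 0.25 × 1.96² / 0.08² = 150.06. The stated 150 reproduces.

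**Inputs.**
- Allocation: 30 of 150 per country, so 20% each (Table 4, indicative).
- Real country shares W_c: not given. Assumption: the Table 2 sales shares, which section 9.2 uses as a proxy for MTX experience. France 11.2, Germany 10.9, Greece 5.4, Poland 10.6, Sweden 7.0; sum 45.1. Rescaled: 24.8%, 24.2%, 12.0%, 23.5%, 15.5%.
- Country proportions p_c: not known, so varied.
- Subsample spread equally over the five countries (assumption).

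**Distortion of the unweighted pooled proportion** = Σ 0.2·p_c − Σ W_c·p_c.

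It is largest for a given gap when France, Germany and Poland (above 20% under the proxy) stand on one side and Greece and Sweden on the other. The first group has 60% of the sample and 32.7/45.1 = 72.5% of the proxy population. The difference is 12.5 percentage points of share, so the distortion is at most 12.5% of the gap.

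| Greece, Sweden | Others | Unweighted | Weighted (proxy) | Difference |
|---|---|---|---|---|
| 80% | 80% | 80.0% | 80.0% | 0 |
| 70% | 90% | 82.0% | 84.5% | −2.5 points |
| 60% | 90% | 78.0% | 81.75% | −3.75 points |
| 50% | 90% | 74.0% | 79.0% | −5.0 points |

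Example, third row: 0.6 × 90 + 0.4 × 60 = 78.0; 0.725 × 90 + 0.275 × 60 = 81.75.

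**More skewed shares (assumed; order France/Germany/Greece/Poland/Sweden).** With 35/35/5/20/5, Greece and Sweden hold 10%, and the difference is −6.0 points for 70% against 90% and −9.0 for 60% against 90%. With 30/35/8/22/5 they hold 13%, and the differences are −5.4 and −8.1.

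**Cost in precision.** Kish factor = 5·ΣW_c². Under the proxy it is 1.069, and √1.069 = 1.034, so intervals are about 3% wider. At P = 50% the 95% margin moves from 17.9 to 18.5 points at n = 30, and from 12.7 to 13.1 at n = 60. Under the two skewed sets the factors are 1.45 and 1.349, so intervals are about 20% and 16% wider.

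**Against sampling error.** The unweighted margin is 17.9 points at n = 30 and 11.3 at n = 75. The distortions above are smaller than that, but unlike sampling error they do not shrink as n grows.

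**The case against.** Four points on the other side have weight.

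1. The limitation is disclosed where the rule is set: subsample figures are offered as a description of the sample. A reader might infer that they could not be compared with anything else in the report. That does not follow, because unweighted full-sample results are reported too and give a like-for-like comparison. What is missing is a subsample figure to set beside the weighted overall result, which section 9.5.3 prefers.

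2. A reader might infer that the main findings are affected, for instance by route or specialty. The protocol does not support this. Endpoints are assessed overall and by country (section 9.7.1), and the ENCePP checklist in Annex 3 marks stratified analyses as not applicable. The pooled subsamples plainly visible are descriptive profiles and complementary questions outside the assessment of success. Whether items for oral users or country-specific materials are routed cannot be settled, since the questionnaires are stand-alone documents.

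3. The country mix of a real subsample will not be exactly 20% each. Specialties differ by country: Annex 2 lists no general practitioners for Sweden and no dermatologists for Poland. The booster rule in section 9.2.4.4 can also change the allocation. The figures above illustrate size and do not predict any particular table.

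4. Section 9.2.4 says the survey was not designed to be representative by age, gender or indication. Country weights do not repair that, so some caution about projecting subsamples is fair. It calls for a caveat. It does not justify leaving in a distortion that the weights can remove.

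**Conclusion.** The point holds as a flaw in reasoning and reporting. The exclusion is unconditional, its stated example concerns precision rather than validity, and it conflicts with the protocol's own case for weighting. Subsamples pooled over countries may be exposed to the country-mix distortion.

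The wording allows the tempting reading that every such result is biased. That goes too far: a distortion needs both country shares that differ from the sample mix and results that differ by country. Under the sales proxy and an equal spread it is at most about 12.5% of the gap between country proportions, or 2.5 to 5 points for gaps of 20 to 40 points. Figures near 9 points require a 30-point gap and an assumed 10% share for Greece and Sweden together, against 27.5% under the proxy. Nor should the 78.0% against 81.75% example be read as overturning a success conclusion at the 80% threshold. It is a subsample illustration, and the full-sample endpoint results are weighted.

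The consequence is modest and, on the visible text, falls mainly on descriptive tables. The correction is cheap enough to be worth making.

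**What to change.** Replace the blanket exclusion in section 9.5.3 as follows:
- For any subsample pooled over countries, report the weighted domain estimate, with a confidence interval based on the full-sample design, beside the unweighted n and percentage.
- State a minimum n and flag estimates below it as imprecise.
- Keep unweighted-only results for subsamples within a single country.
- Say what counts as a subsample, so that items limited to oral users or to certain countries are clearly covered.

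The weight variable is already planned for every completed questionnaire, so the work is about one extra table column. The price is wider intervals: about 3% under the proxy shares and about 16 to 20% under the more skewed shares examined.
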